8.10. Health Economics Data and Medical Resource Utilization

Health economics data and medical resource utilization will not be collected or evaluated in this study.

 Page 57 of 97	
Alexion Confidential	

9. STATISTICAL CONSIDERATIONS

9.1. Statistical Hypotheses

No statistical hypotheses are planned for this study.

9.2. Sample Size Determination

The sample size is empiric and selected to support assessment of safety, tolerability, and PK parameters. Approximately 15 participants will be enrolled to allow for at least 9 participants (3 per cohort) to "complete" (ie, participant completed EoT assessments, all PK/PD sampling was performed within window, and all doses were received per the SoA) the study. It is expected that 9 "completed" participants will support adequate characterization of safety, tolerability, and PK/PD for the ALXN1850 compound.

9.3. **Populations for Analyses**

Population	Description
Safety Set	All participants who receive any amount of study drug will be included in the Safety Set. Participants will be analyzed according to the study drug received.
Pharmacokinetic Set	All treated participants for whom the PK profile of ALXN1850 can be adequately characterized will be included in the PK Set. Pharmacokinetic analyses will be based upon the study drug received.
Pharmacodynamic Set	All treated participants for whom the PD profile of ALXN1850 can be adequately characterized will be included in the PD Set.
Immunogenicity Set	All treated participants for whom pre and postdose anti-ALXN1850 antibody samples are obtained will be included in the Immunogenicity Set.

The population sets used for analysis sets are defined in the following:

9.4. Statistical Analyses

In general, descriptive statistics for continuous variables will include number of non-missing values, arithmetic mean, standard deviation, median, minimum, and maximum. Descriptive statistics for PK parameters will include number of observations, arithmetic mean, standard deviation, arithmetic coefficient of variation (%CV), median, minimum, maximum, geometric mean, and geometric %CV. Categorical variables will be summarized using percentages and frequency counts, by cohort and time point.

A statistical analysis plan (SAP) will be developed and finalized before first data cutoff/database lock and will further describe the participant populations to be included in the analyses, and procedures for accounting for missing, unused, and spurious data as appropriate. This section is a high-level summary of the planned statistical analyses of the primary and secondary endpoints.

9.4.1. Efficacy Analyses

No efficacy analyses will be performed for this study.

Page 58 of 97	
Alexion Confidential	

9.4.2. Safety Analyses

The primary objective of the study is to assess the safety and tolerability of ALXN1850. The endpoints to support the primary objective include incidence of TEAEs and treatment-emergent serious adverse events (TESAEs). The incidence of TEAEs and TESAEs will be summarized by System Organ Class (SOC) and Preferred Term by administration and cohort overall, by severity, and by relationship to study intervention. Adverse events will be categorized by the type of administration being received at the date of onset (ie, IV or SC). Treatment-emergent AEs and TESAEs resulting in withdrawal from the study will be listed. Participants having multiple AEs within a category (eg, overall, SOC, Preferred Term) will be counted once in that category. For severity tables, a participant's most severe event within a category will be counted. Adverse events of special interest will be analyzed similarly.

Changes from baseline in vital signs and laboratory assessments (as displayed in Table 7) will be summarized by visit for each cohort. Laboratory parameter values will be graded based on the National Cancer Institute CTCAE grading for severity (v5.0, published 27 Nov 2017). Shift tables by treatment group will be produced for these laboratory parameters. These tables will summarize the number of participants with each baseline grade relative to the normal ranges and changes to the worst highest grade assessed postdose during the study.

Electrocardiogram parameters will be measured at the specified time points, including heart rate, PR, RR, QRS, QT, and QTcF intervals. The average of the triplicate ECG readings at the time points collected will be calculated, and changes from pretreatment baseline values will be assessed.

An outlier analysis will be performed that will summarize the frequency and percentage of participants who meet any of the following outlier criteria at each visit.

- QT, QTcF interval > 450 msec
- QT, QTcF interval > 480 msec
- QT, QTcF interval > 500 msec
- QT, QTcF interval increases from baseline > 30 msec
- QT, QTcF interval increases from baseline > 60 msec

Physical examination results will be classified as Normal, Abnormal Not Clinically Significant (NCS), Abnormal Clinically Significant (CS), and Not Examined. The results will be summarized by visit for each administration.

All concomitant medications will be coded using the World Health Organization (WHO) Drug Dictionary, and the frequency and percentage of concomitant medications will be summarized.

While safety analyses will be performed on the Safety Set (defined in Section 9.3), all safety data collected will be listed by participant.

Page 59 of 97
Alexion Confidential

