7. DISCONTINUATION OF STUDY INTERVENTION AND PARTICIPANT DISCONTINUATION/WITHDRAWAL

Stopping rules provide explicit guidance for the discontinuation of treatment cohorts and discontinuation of individual participants. The following rule sets apply to TEAEs that are assessed by the Investigator to be related to study drug (unless specified otherwise). While stopping rules provide an explicit guide for dose discontinuation, the Investigator and/or Alexion may elect to discontinue dosing at any time. Dose continuation or escalation will proceed as scheduled and the study will continue as planned provided no prespecified toxicity events occur (as determined by the SRC).

The entire study will be suspended if any severe or life-threatening treatment-emergent serious adverse events (TESAEs) occur.

Participants who do not complete the study but have been dosed should make every effort to undergo all scheduled safety, PK, and PD evaluations required by the protocol (refer to SoA, Section 1.3) in relation to the last dose they received. Alexion and site monitor will be notified as soon as possible.

If a participant withdraws consent and is unwilling to attend all scheduled procedures, every attempt will be made to encourage them to complete the ED visit at a minimum.

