7.1. Discontinuation of Study Intervention

7.1.1. Cohort Stopping Rules

Within cohort dosing will be temporarily halted if any of the following are observed:

- Two or more participants experience CTCAE Grade 2 TEAE (excluding ISR and injection/infusion associated reactions) with the same PT or medical concept that are considered to be related to study drug and do not show signs of reversibility by the following visit.
- One participant experiences a CTCAE Grade 3 (or higher) TEAE considered to be related to study drug.
- Severe (Grade 3) injection site reaction in more than 50% of a cohort, assessed by the Investigator to be related to the study drug
- The PK stopping limit defined as 50% of the NOAEL exposure (mean C_{max} and AUC_{0-168h} values) established in the GLP 4-week monkey toxicology study. This stopping rule will only be assessed before dose-escalating between Cohort 2 and Cohort 3.

In the event of suspension of dosing, continuation of the study will require a protocol amendment.

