Injection/infusion-associated reactions are defined as systemic AEs (eg, fever, chills, flushing, alterations in heart rate and blood pressure, dyspnea, nausea, vomiting, diarrhea, and generalized skin rashes) oc curring during or within 24 hours of the start of IV or SC injection/infusion that are assessed by the Investigator to be related to the study drug.

An overview summary of TEAEs will be provided and will include number and percentage of participants:

- With at least 1 TEAE
- With at least 1 TEAE related to study drug
- With at least 1 TESAE
- With at least 1 TESAE related to study drug
- Drug withdrawn due to a TEAE
- Drug withdrawn due to a TEAE related to study drug
- Who died
- With at least 1 injection/infusion-site reactions
- With at least 1 injection/infusion-associated reactions
- With at least 1 hypersensitivity reaction

All AE summary tables will be summarized by the most recent type of administration (IV or SC), cohort, and overall (within each cohort and all cohorts combined)

All AEs will be coded using MedDRA (version to be delineated in the CSR). The summary will be presented according to the most recent type of administration (ie, IV or SC) be ing received prior to the AE onset regardless of when the AE ended, and by cohort and overall.

The TEAEs will also be summarized by system organ class (SOC), p referred term (PT), by severity and relationship to study treatment. The TESAEs will also be summarized by SOC, PT, and by relationship to study treatment.

Adverse events of special interest including injection/infusion-site reactions and hypersensitivity including anaphylaxis (injection/infusion-associated reactions [IAR] + hypersensivity) will also be summarized by SOC and PT.

The summary of TEAE, TESAE, and AE of special interest including injection/infusion-site reactions and hypersensitivity including anaphylaxis by SOC and PT will also be repeated by ADA status (ADA negative and ADA positive, and/or pre-existing immunogenicity, treatment-emergent ADA responses, and treatment-boosted ADA responses if data permits).

In the summary tables where both SOC and PT are presented, the default ordering of SOC will be alphabetical and the default ordering for PT will be most prevalent (using percentage) PT within each SOC based on Total column. For PTs with the same number of participants, they should be further sorted by number of events and then alphabetically.

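### Protocol 9.4.2 promises serious and special-interest adverse events by severity, but SAP 9.1 gives severity only for TEAEs as a whole and does not declare the change

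*Protocol*

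**What the plan says.** **Protocol 9.4.2.** The rule for adverse events is that "The incidence of TEAEs and TESAEs will be summarized by System Organ Class (SOC) and Preferred Term by administration and cohort overall, by severity", followed by relationship to treatment. The counting rule is "For severity tables, a participant's most severe event within a category will be counted". For special-interest events (AESIs): "Adverse events of special interest will be analyzed similarly". Protocol 8.3.6 names injection site reactions and injection-associated reactions as AESIs and points to the intensity grading in 10.3.4 for both.

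**SAP 9.1.** TEAEs are summarized by SOC and preferred term (PT), "by severity and relationship to study treatment". The next sentence reads "The TESAEs will also be summarized by SOC, PT, and by relationship to study treatment". For AESIs, site reactions and "hypersensitivity including anaphylaxis (injection/infusion-associated reactions [IAR] + hypersensivity) will also be summarized by SOC and PT".

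The same SAP section counts a participant once, at the worst grade, within each route of administration. It also plans an overview table of participants with at least one TESAE, site reaction, associated reaction or hypersensitivity reaction. TEAEs, TESAEs, site reactions and hypersensitivity are each to be listed separately.

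**The concern.** The protocol makes one commitment covering three classes of event, and the SAP keeps its severity part for one of them. TESAE incidence is one of the two primary endpoints. Site-reaction tolerability matters for this molecule in particular: Protocol 2.1 gives the site-reaction burden of the existing therapy as a reason for developing it.

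Grade within these same classes is also something the protocol treats as important. Section 7 states "The entire study will be suspended if any severe or life-threatening treatment-emergent serious adverse events (TESAEs) occur", and 7.1.1 includes "Severe (Grade 3) injection site reaction in more than 50% of a cohort, assessed by the Investigator to be related to the study drug". A reader of the study report would expect a table showing how many participants had a serious event, or a site reaction, at each worst grade. The SAP plans no such table.

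**Working it through.** No sample size, power or error rate is involved, and the plan states no figure to reproduce. The check compares texts, with one small count.

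**1. Planned summaries side by side**

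| Event class | Protocol 9.4.2 | SAP 9.1 |
|---|---|---|
| TEAE | SOC/PT, severity, relationship | SOC/PT, severity, relationship |
| TESAE | SOC/PT, severity, relationship | SOC/PT, relationship |
| AESI | same as above | SOC/PT |

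Severity is missing for two classes of three. AESIs also lose relationship. That matters little, because SAP 9.1 defines site and associated reactions as events judged related; only other hypersensitivity events are affected.

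**2. Is severity restored or the change declared elsewhere?** The overview table gives ungraded counts. SAP 9.8 summarizes scheduled site evaluations by time point and mentions neither adverse-event grade nor worst grade per participant. SAP 1 and 14 send departures from the SAP to the study report. They do not cover a departure of the SAP from the protocol, so this one would go unrecorded.

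**3. Can the counts be recovered from the TEAE severity table?**

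- *Serious events.* Protocol 10.3.4 keeps seriousness and severity apart. The TEAE table pools serious and non-serious events, so a Grade 3 cell does not show how many participants had a Grade 3 serious event.
- *Site reactions.* The group is defined by location and relatedness, so it may span several PTs. If the PT rows show k1, k2, ... participants at a grade in a cohort of n, the number of distinct participants N satisfies max(k) ≤ N ≤ min(sum of k, n). As an assumed example, take three PTs with one Grade 3 entry each and n = 5, the approximate planned cohort size. Then max = 1 and min(3, 5) = 3, so N is 1, 2 or 3: 1/5 = 20%, 2/5 = 40% or 3/5 = 60%. A SOC row does not settle it, because it also counts any other term in that SOC.

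**4. The halt rules against the planned tables**

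| Rule (Protocol 7, 7.1.1, 7.1.2) | Where SAP 9.1 shows the grade |
|---|---|
| Related Grade 2 TEAE rules (cohort, individual) | TEAE severity table |
| Related Grade 3 or higher TEAE rules (cohort, individual) | TEAE severity table |
| Severe or life-threatening TESAE (whole study) | No dedicated count |
| Grade 3 site reaction (cohort, individual) | By PT among TEAEs; no group count |

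The SAP does not say whether severity is crossed with relationship in the TEAE table. The last two rows show where a table is missing; they do not show that a rule cannot be applied. Protocol 7 leaves it to the Safety Review Committee to determine whether a prespecified toxicity event has occurred.

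**The case against.** The best reply is that little is lost.

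- **Grades are still tabulated.** A TESAE or AESI after first dose is a TEAE, so its grade enters the TEAE severity table. This stands. A reader might infer that these grades are never tabulated, and the documents do not support that. What is absent is the count of participants at worst grade within the serious and special-interest groups.
- **The halt rules do not run on SAP tables.** This stands too. A reader might infer that stopping decisions are weakened. However, the committee applies the rules during the study. Protocol 9.6 requires an ad hoc meeting within 48 hours of a treatment-emergent serious event, and SAP 13 plans no formal interim analysis and refers the escalation review to separate data snapshots.
- **The primary endpoint is reported.** It is defined as incidence, without severity, and SAP 9.1 gives TESAE incidence in full. A reader might infer that the endpoint itself is compromised; it is not. What is cut is the breakdown that the protocol attached to it.
- **Listings allow a hand count.** With about 5 participants per cohort this is feasible if the listings carry grade, which the SAP does not state. A listing still does not meet a commitment to summarize.
- **The protocol text is only a high-level summary.** Protocol 9.4 says so, and says the SAP will describe the analyses further. That allows added detail, not the unannounced removal of a named summary.
- **The 20% to 60% range is constructed.** Agreed. It shows that PT rows cannot be added up; it predicts nothing. Nor should it be read as deciding the 50% rule. Only the Grade 2 bullet in 7.1.1 excludes site reactions, so on a literal reading one related Grade 3 event already meets another bullet. How those bullets fit together needs reconciling separately, and this point takes no position on it.

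**Conclusion.** The mismatch is real and modest. Protocol 9.4.2 commits to severity for three event classes; SAP 9.1 delivers it for TEAEs only and does not say that it has changed the plan. Worst-grade participant counts for serious events and for site or associated reactions have no planned table, and the pooled TEAE table cannot be relied on to supply them.

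The consequence is incomplete reporting. Trial conduct, the halt rules and the reporting of TESAE incidence are unaffected.

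The conclusion rests on three things: reading the protocol's instruction on special-interest events as including severity; site reactions possibly being coded to more than one PT; and the absence of a restoring table in the SAP text supplied. If all site reactions were coded to a single PT, the TEAE table would give the site-reaction count, but the gap for serious events would remain.

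**What to change.** In SAP 9.1:

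1. Change the TESAE sentence so that the summary is by SOC, PT, severity and relationship.
2. Change the AESI sentence so that the summary is by SOC, PT and severity.
3. For each AESI group the SAP already defines (site reactions; hypersensitivity including associated reactions), add a row by cohort and route that counts each participant once at worst grade across all terms in the group.

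Alternatively, state in the SAP that severity summaries for TESAEs and AESIs are omitted, and justify this as a departure from Protocol 9.4.2.

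The cost is some SAP wording and a few extra tables, many of whose cells will probably be empty at this sample size. Protocol 10.3.4 already requires a grade for every adverse event, so no new data are needed.

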9.4.3. Other Analyses

9.4.3.1. Pharmacokinetic Analyses

All PK analyses will be performed on the PK Set and will be reported by each cohort. The individual plasma concentration data from participants who receive ALXN1850 with actual sampling dates and times will be used to derive the PK parameters by noncompartmental analyses methods using Phoenix WinNonlin 8 or higher.

PK Parameters	Definition
C _{max}	Maximum observed plasma concentration
t _{max}	Time to maximum observed plasma concentration
AUCt	Area under the plasma concentration versus time curve from time 0 to the last quantifiable concentration
AUC _{tau}	Area under the plasma concentration versus time curve during the dosing interval
AUC _∞	Area under the plasma concentration versus time curve from time 0 (dosing) to time infinity
t _{1/2}	Terminal elimination half-life
λ _z	Terminal-phase elimination rate constant
CL or CL/F	Total body clearance
Vd or Vd/F	Volume of distribution
R	Subcutaneous accumulation ratio (Dose 3/Dose 1)
F	Absolute bioavailability after subcutaneous administration

The following PK parameters will be derived:

9.4.3.2. Pharmacodynamic Analyses

All PD analyses will be performed on the PD Set and will be reported by each cohort.

Absolute, change, and percent change from the baseline in plasma PLP, PLP/PL ratio, and PPi concentration versus time data will be presented graphically by treatment over time.

Biomarker assays may be conducted as exploratory analyses on collected samples.

9.4.3.3. Immunogenicity Analysis

Immunogenicity, as measured by ADAs and NAbs to ALXN1850 and asfotase alfa (at Screening, only for participants who have previously received asfotase alfa), will be summarized.

Participants who are positive for ADAs at the last assessment of the study will be given options to enable further monitoring of their ADA values after the end of the study; these options may include enrollment in the Global HPP Registry.

9.4.3.4. Exploratory Analysis

Change in ionized calcium, phosphorus, magnesium, PTH, PA, sCTX, P1NP, and osteocalcin versus time will be presented graphically by treatment over time.

Page 60 of 97	
Alexion Confidential	

9.5. Interim Analyses

Interim analyses may be performed as needed. In particular, an interim analysis may be conducted for each cohort at the end of the Day 29 after all participants in the corresponding cohort have completed or withdrawn. This analysis will allow for further evaluation of the doses and for subsequent ALXN1850 Phase 2/3 studies planning purpose.

The SAP will describe the planned interim analyses in greater detail.

9.6. Safety Review Committee (SRC)

An SRC consisting of, but not limited to, the Investigator, Safety Monitor, Medical Monitor, Study Statistician, and Clinical Pharmacologist, will evaluate the study data at prespecified time points for participant safety and make recommendations on dose escalation, dose modification, or termination of the study. The SRC charter will include a description of membership, schedule of meetings, data required for each safety review, and requirements for documenting meeting discussions and outcome. For more details refer to Section 6.6.

In addition to planned meetings, ad hoc SRC meetings may be held to discuss urgent issues should the need arise. The ad hoc SRC must convene within 48 hours in the case of a treatment-emergent SAE or the withdrawal of any participant due to an adverse reaction.

 $P_{acce} 61 \text{ of } 07$	
Page 61 of 97 Alexion Confidential	
Alexion Confidential	

10. SUPPORTING DOCUMENTATION AND OPERATIONAL CONSIDERATIONS

10.1. Regulatory, Ethical, and Study Oversight Considerations

10.1.1. Regulatory and Ethical Considerations

- This study will be conducted in accordance with the protocol and the following:
 - Consensus ethical principles derived from international guidelines including the Declaration of Helsinki and CIOMS International Ethical Guidelines
 - Applicable International Council for Harmonisation of Technical Requirements for Pharmaceuticals for Human Use (ICH) Good Clinical Practice (GCP) Guidelines
 - Applicable laws and regulations
- The protocol, substantial protocol amendments, ICF, IB, and other relevant documents (eg, advertisements) must be submitted to an IRB/IEC by the Investigator and reviewed and approved by the IRB/IEC before the study is initiated.
- Any substantial amendments to the protocol will require IRB/IEC approval before implementation of changes made to the study design, except for changes necessary to eliminate an immediate hazard to study participants.
- The Investigator will be responsible for the following:
 - Providing written summaries of the status of the study to the IRB/IEC annually or more frequently in accordance with the requirements, policies, and procedures established by the IRB/IEC
 - Notifying the IRB/IEC of SAEs or other significant safety findings as required by IRB/IEC procedures
 - Providing oversight of the conduct of the study at the site and adherence to requirements of 21 CFR, ICH guidelines, the IRB/IEC, Directive 2001/20/EC, European regulation 536/2014 for clinical studies (if applicable), and all other applicable local regulations

